Happy Family, Healthy Kids: An Intergenerational Program to Promote Healthy Eating

Habits

NCT04183179

Date: August 23, 2022

Theoretical Framework

The “Happy Family, Healthy Kids” program was grounded in the Actor-Partner Interdependence Model (Cook & Kenny, 2005), the Allostatic Load Model (McEwen, 2000), and the Transactional Theory of Stress and Coping (Lazarus & Folkman, 1987). The Actor-Partner Interdependence Model has been used in lifestyle behavioral and mental health interventions to better understand the intergenerational interactions and relationships inside a family (Braithwaite & Fincham, 2011; Vedanthan et al., 2016). The Actor-Partner Interdependence Model demonstrates the bidirectional relationship between preschoolers and parents: 1) actor effects within preschoolers or parents and 2) partner effects between preschoolers and parents (Cook & Kenny, 2005).

According to the Allostatic Load Model (McEwen, 2000) and the Transactional Theory of Stress and Coping (Lazarus & Folkman, 1987), to respond to stress, individuals first cognitively appraise external stressors according to their harm, threat, or challenge. Then, they respond to the appraised stressors with different coping strategies including problem-focused coping, emotion-focused coping, and avoidant coping. Problem-focused coping focuses on making cognitive and behavioral effort to change a stressful situation in a positive way (Lazarus & Folkman, 1987). Emotion-focused coping involves regulating difficult emotions such as anger, fear, anxiety, depression, frustration, and sadness that are associated with stress (Lazarus & Folkman, 1987). Avoidant coping is a maladaptive form of coping that includes denying or avoiding the stressful situations or feelings to temporarily reduce stress (Penley, 2002). When the selected coping strategies fail to manage the external stressors, the cumulative burden of chronic stress (allostatic load) can lead to poor health outcomes such as obesity, cardiovascular diseases, anxiety, and depression (Guidi et al., 2021; Lazarus & Folkman, 1987; McEwen, 2000).

Fortunately, maintaining a healthy lifestyle, such as having healthy diet, is associated with lower allostatic load, resulting in improved physical and mental health (Forrester et al., 2019; Mattei et al., 2013). Based on information from the theory and models, the “Happy Family, Healthy Kids” program focused on the connections between F/V intake and mental health to strengthen both preschoolers’ and parents’ adaptive coping strategies (e.g., mindful eating) and reduce maladaptive coping strategies (e.g., emotional eating) to enhance their overall well-being.

Methods

Study Design, Setting, and Sample

A one-group quasi-experimental study was conducted in 13 Michigan Head Start centers across two academic years. In Year 1, three urban Head Start centers (eight classrooms) and three rural Head Start centers (five classrooms) participated. In Year 2, four urban Head Start centers (five classrooms) and three rural Head Start centers (five classrooms) participated. The total enrollment from the 23 Head Start classrooms was 374 preschoolers, and 127 (34%) of the families were initially interested in participating in the study. Of the 127 families, 20 were excluded due to not meeting the inclusion criteria or declining to participate or for other reasons. A total of 107 parent-preschooler dyads were enrolled in the study, but four preschoolers did not receive the program due to being dropped out of the Head Start programs. The study flow diagram is presented in Figure 1.

We recruited parent-preschooler dyads using the following two strategies: 1) Head Start teachers and family engagement specialists shared the recruitment flyer with their classroom families; and 2) at urban settings, the study project manager and trained research assistants recruited participants and answered questions in-person during daycare drop-offs and pick-ups.

A \$5 e-gift card was distributed to the families who completed the enrollment and screening survey.

Sample size was estimated using the freely available G*Power software. With the study design being one-group quasi-experimental and a significance level of 0.05, a sample size of 90 would achieve 80% study power to identify a small effect size of 0.30, and a sample size of 102 would achieve 85% power. Inclusion criteria were: 1) child was 3-5 years old and enrolled in a participating Head Start program; 2) parent was the primary caregiver for the child, had at least weekly Internet access, and was willing to use Facebook to participate; 3) dyad was able to speak and understand English; and 4) parental consent and child assent (if child was five years old) were obtained. Preschoolers were excluded if they had any medical conditions preventing them from participating in dietary changes. University Institutional Review Board approved the project, and parents' consent and 5-year-old preschoolers' verbal assent were obtained.

“Happy Family, Healthy Kids” Program

Table 1 demonstrates the three components of the 14-week healthy eating and stress management program. Each participating family received a crockpot and a program “Healthy Tasty Cookbook” to promote healthy family meals at home, an adult and a child MyPlate plates to encourage appropriate portion size and healthy eating habits, and a community resource booklet to share community resources on healthy eating (e.g., local farmers markets) and stress management (e.g., mindfulness classes, local trails for walking in nature).

Measurements and Data Collection

As demonstrated in Table 2, reliable and valid instruments were selected to assess program outcomes at two time points: baseline and post-program. Parents completed an online survey measuring their nutrition knowledge, self-efficacy, support, child feeding

beliefs/attitudes/practices, food resource management behavior, perceived stress, coping strategies, dietary intake, home eating environment, emotional eating, and food insecurity via Qualtrics. A face-to-face appointment was scheduled with each parent-preschooler dyad to objectively measure their height to the nearest 0.1cm using the Shorr board, weight to the nearest 0.1kg using the Seca 874 scale, % body fat to the nearest 0.1% using the BF-689 body fat/body water monitor for preschoolers and BC-533 InnerScan body composition monitor for parents, and parents' BP to the nearest 1mmHg using the Omron HEM-705-CP digital BP monitor.

For height, weight, and % body fat measurements, participants were asked to remove shoes, socks, or bulky clothes. To avoid interference with height measurements, participants were asked to remove their accessories or change hairstyles (no ponytail) when applicable. If a participant refused, trained data collectors would obtain the height measurement as well as measure hairdo height (using small, flexible plastic ruler) and record both types of information on the data collection form. Each participant's biological sex, age, and height in cm were entered into the monitor for measuring % body fat. Trained data collectors then instructed participants to step onto the monitor surface and align feet with the four electrodes. The protocol by the American Heart Association (2020) was followed for BP measurement. Parents' left arms were used for BP measurement unless having a prior surgery or injury.

To increase reliability for measuring height, weight, % body fat, and BP, two measurements were taken. A third measurement was taken when the first two measurements differed by ≥ 0.5 cm for height, ≥ 0.5 kg for weight, $\geq 1\%$ for % body fat, and ≥ 5 mmHg for BP. The data collection process was repeated by another data collector when the third measurement was ≥ 0.5 cm, ≥ 0.5 kg, $\geq 1\%$, and ≥ 5 mmHg away from the first two measurements. The average of the two closest measurements was calculated as the final value. The online SAS program for

Centers for Disease Control and Prevention Growth Charts (2021) was applied to calculate preschoolers' BMI for age and sex.

In Year 2, an instrument called the Veggie Meter® was utilized to assess skin carotenoids as an indicator for F/V intake. Biologically, carotenoid levels in serum/plasma have been used as a biomarker to estimate F/V intake (Ferrari et al., 2005). However, this invasive approach due to the drawing of blood can generate needle-related stress, anxiety, insecurity, and fear among participants (Soares da Silva, 2016). The skin carotenoid score measured by resonance Raman spectroscopy (the Veggie Meter®; Longevity Link, Salt Lake City, UT) was proposed as a non-invasive biomarker for F/V intake given its high correlation ($r=0.70-0.72$) with carotenoid levels in blood plasma/serum (Aguilar et al., 2014; Jahns et al., 2014). To assess skin carotenoids in this study, each participant's non-dominant index finger was used, and the average of three scans was recorded as the final score.

Table 1. The 14-week “Happy Family, Healthy Kids” program

Component	Descriptions
A 14-week parent component	
• A 14-week Facebook-based program with weekly videos and flyers providing life stress management and eating behavioral change strategies and 4 weekly habit-formation tasks to create a happier and healthier home environment for preschoolers.• 3 virtual meetings (weeks 1, 7, & 14) to establish personal connections and communication networks among parents, discuss strategies, and share community resources to support behavioral changes at home.• 3 motivational text messages (Monday, Wednesday, Friday) per week for 14 weeks to increase parents’ motivation for making healthy eating behavioral changes at home and encourage them to positively manage stress.
A parent-preschooler learning component	Sending weekly preschooler letters (total 13 letters) to each parent privately via Facebook messenger by the research team to share the preschooler’s experiences of learning at school and his/her stated interests for a healthy diet at home, and to ask parents to respond to the letters.
A 14-week Head Start center-based preschooler component	Helping preschoolers establish mindful healthy eating habits via weekly healthy diet participatory learning (e.g., food taste test activity) following the “Eat My ABCs” curriculum.

References

Aguilar, S. S., Wengreen, H. J., Lefevre, M., Madden, G. J., & Gast, J. (2014). Skin carotenoids: A biomarker of fruit and vegetable intake in children. *J Acad Nutr Diet*, 114(8), 1174-1180. <https://doi.org/10.1016/j.jand.2014.04.026>

American Heart Association. (2020). *How to accurately measure blood pressure at home*. Retrieved September 18, 2022 from <https://www.heart.org/en/news/2020/05/22/how-to-accurately-measure-blood-pressure-at-home>

Braithwaite, S. R., & Fincham, F. D. (2011). Computer-based dissemination: A randomized clinical trial of ePREP using the actor partner interdependence model. *Behaviour Research and Therapy*, 49(2), 126-131. <https://doi.org/https://doi.org/10.1016/j.brat.2010.11.002>

Centers for Disease Control and Prevention. (2021). *About child & teen BMI*. Retrieved February 20, 2023 from https://www.cdc.gov/healthyweight/assessing/bmi/childrens_bmi/about_childrens_bmi.html

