Happy Family, Healthy Kids: An Intergenerational Program to Promote Healthy Eating

Habits

NCT04183179

Date: August 23, 2022

Data Analysis

The IBM SPSS Statistics 27 was used to perform all data analyses. Descriptive statistics were applied to describe variables' means, standard deviations, ranges, frequencies, and percentages. To compare differences by study year or setting, independent-samples t-test was used when the variable was continuous, and Chi-square test or Fisher's exact test was utilized when the variable was categorical. The Little's Test was used to examine whether the data were missing completely at random. The missing data rates ranged from 0% to 27.1%. The Little's test result was not significant ($\chi^2=2939.24, p=1.00$), indicating the data were missed completely at random. Multiple imputation ($m=20$) was performed on all demographic and outcome variables. Analyses were performed on each imputed dataset and the results were pooled using Rubin's rule. Robustness of the results was examined by comparing results before and after imputation.

Paired-samples t-tests were performed to examine the outcome changes from baseline to post-program in each study year across urban and rural settings. To estimate effect size, Cohen's d was calculated to describe program effects as small=0.20, medium=0.50, and large=0.80. To explore the program effects by year and setting, general linear model was employed by treating post-program outcome as the dependent variable, baseline outcome as the covariate, and study year and setting as the fixed factors. As this study was an exploratory pilot non-randomized trial aiming to generate the effect sizes for future confirmatory studies, multiple testing adjustments were not used.

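### The only stated power (80% at 90, 85% at 102) fits one pre-post test on the whole sample, but the SAP states its paired tests only within each study year

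*Protocol*

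**What the plan says.** The Protocol gives one power statement, in Study Design, Setting, and Sample. It opens "With the study design being one-group quasi-experimental and a significance level of 0.05" and continues that "a sample size of 90 would achieve 80% study power to identify a small effect size of 0.30", with 102 giving 85%. It names no test, sidedness or outcome, and does not mention study years.

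The same section gives the size achieved over both years: "A total of 107 parent-preschooler dyads were enrolled in the study", of whom "four preschoolers did not receive the program due to being dropped out of the Head Start programs". Dyads per year are not given.

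The SAP (Data Analysis, second paragraph) states the pre-post tests: "Paired-samples t-tests were performed to examine the outcome changes from baseline to post-program in each study year across urban and rural settings". Cohen's d "was calculated to describe program effects as small=0.20, medium=0.50, and large=0.80". The one model that uses both years has a different purpose: "To explore the program effects by year and setting, general linear model was employed", with the post-program value as outcome, adjusted for baseline, and year and setting as factors. The study is described as "aiming to generate the effect sizes for future confirmatory studies".

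**The concern.** A reader with a single power figure will attach it to the pre-post tests that are reported. Those tests are run on each year's dyads separately, and 107 dyads cannot supply 90 to each of two years.

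Precision is also at stake. The effect sizes are meant to feed later trials. As written, Cohen's d goes with the year-specific changes, no confidence interval is stated for it, and no pre-post effect size is stated for the whole sample. A later trial would be planned on two noisier estimates per outcome when one firmer estimate is available from the same data.

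**Working it through.** **Inputs.** From the Protocol: effect size 0.30, alpha 0.05, N of 90 and 102, 107 dyads enrolled, 4 preschoolers who did not receive the program. From the SAP: paired t-tests within each study year. Assumptions: 0.30 is in SDs of the paired change; tests are two-sided; pairs are complete; clustering is ignored; urban and rural dyads are pooled within a year, which is the reading of the SAP sentence that gives more power.

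**Formula.** For n pairs, df = n − 1, noncentrality = 0.30 × √n, and power = P(|T| > t(0.975, n − 1)) under the noncentral t distribution.

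**Step 1: the plan's own figures.**
- n = 90: noncentrality 0.30 × √90 = 2.85, power 0.804. n = 89 gives 0.799, so 90 is the smallest N for 80%.
- n = 102: noncentrality 0.30 × √102 = 3.03, power 0.851. n = 101 gives 0.848, so 102 is the smallest N for 85%.
- A one-sided test would need only 71 and 82.

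Both stated figures reproduce exactly on one undivided sample.

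**Step 2: can each year reach them?** Two years at 90 need 90 + 90 = 180 dyads, more than 107. If one year had 90, the other would have 107 − 90 = 17.

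**Step 3: a bound that needs no assumed split.** However 107 is divided, the smaller year has at most 53 (107 / 2 = 53.5, rounded down). Without the four dyads whose preschooler did not receive the program, the total is 107 − 4 = 103 and the smaller year has at most 51.

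The half-width below is t(0.975, n − 1)/√n. The interval for an observed effect size of 0.30 comes from inverting the noncentral t.

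| n | Power at 0.30 | Effect detectable with 80% power | 95% half-width (SD of change) | 95% CI for an observed 0.30 |
|---|---|---|---|---|
| 107 (both years) | 0.868 | 0.273 | 0.192 | 0.106 to 0.493 |
| 103 (both years) | 0.854 | 0.279 | 0.195 | 0.102 to 0.497 |
| 53 (best case, smaller year of 107) | 0.573 | 0.392 | 0.276 | 0.023 to 0.574 |
| 51 (best case, smaller year of 103) | 0.556 | 0.400 | 0.281 | 0.018 to 0.579 |

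Simulated power (200,000 runs at each n) agrees to within 0.003.

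**Step 4: illustrative splits (assumed).** Classrooms numbered 8 + 5 = 13 in Year 1 and 5 + 5 = 10 in Year 2. Dividing the 107 dyads 13:10 gives 60 and 47, with power 63% and 52%. A 64/43 split gives 66% and 49%.

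**Step 5: the general linear model.** Its stated terms compare years and settings, given baseline. No term is put forward as a test of mean change from baseline, so it does not stand in for the missing both-years test. For comparison, a both-years test of mean change adjusted for year and setting (df = n − 3) keeps power at about 0.87 with 107 dyads.

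**The case against.** - **The test is inferred, and not uniquely.** The Protocol names no test. A one-degree-of-freedom F test with Cohen's f = 0.30 also gives 90 and 102, and that family includes the SAP's general linear model. This stands as a caveat. The one-group design, the description of 0.30 as small, and the SAP's use of Cohen's d favour the paired reading. On the F reading the figure would still not describe the year-specific paired tests.
- **No number is wrong, and power per year was never claimed.** Both are true. The fault lies in which analysis the figure belongs to.
- **Silence is not proof.** The SAP is two paragraphs long, and a both-years test may have been intended or run. If so, a sentence saying so and its confidence interval would settle the point.
- **It is an exploratory pilot, already completed.** Year-specific power decides little here, and restating it changes no data. That lowers the stakes. But the SAP uses the exploratory label to justify omitting multiplicity adjustment, and a study meant to produce effect sizes depends on their precision.
- **The bound covers only the smaller year.** Correct. The larger year does better under an uneven split, but it reaches 80% only if the other year has 17 dyads or fewer.

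**Conclusion.** The concern holds. The 80% and 85% are sound for one two-sided paired test over the whole sample, and the SAP does not state that test. For the tests it does state, at least one year has power of at most 57% at an effect of 0.30 (56% on 103 dyads), and its 95% interval is at least about 0.28 SD of change either side, against 0.19 for the whole sample.

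These are best-case figures for the smaller year. They assume complete pairs, no clustering and settings pooled within year. The SAP reports missing data of up to 27.1% but not how many complete pairs each outcome has, so no lower figure is offered. The point should be fixed; it does not invalidate the study.

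**What to change.** 1. **SAP, Data Analysis.** For each outcome measured in both years, add a pre-post estimate and effect size with 95% CI over both years. One way is to regress change on centred year and centred setting, so that the intercept is the mean change, and pool over the 20 imputations by Rubin's rule as already planned. A single paired test over both years would also serve. Label the analysis as added after data collection.
2. **SAP, same paragraph.** Keep the year-specific changes as descriptive, each with its N and 95% CI. Include here the skin carotenoid score, which was measured in Year 2 only.
3. **Protocol, sample size paragraph.** Name the test and its sidedness. State that the 80% and 85% apply to the both-years test only, with complete pairs and no allowance for clustering.

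The cost is a few sentences and one extra model per outcome, with no new data. There are two drawbacks. The added estimate is post hoc, since the SAP already reports observed missingness. The power statement will also read less favourably for the year-specific tests.

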Happy Family, Healthy Kids: An Intergenerational Program to Promote Healthy Eating

Habits

NCT04183179

Date: August 23, 2022

Data Analysis

The IBM SPSS Statistics 27 was used to perform all data analyses. Descriptive statistics were applied to describe variables' means, standard deviations, ranges, frequencies, and percentages. To compare differences by study year or setting, independent-samples t-test was used when the variable was continuous, and Chi-square test or Fisher's exact test was utilized when the variable was categorical. The Little's Test was used to examine whether the data were missing completely at random. The missing data rates ranged from 0% to 27.1%. The Little's test result was not significant ($\chi^2=2939.24, p=1.00$), indicating the data were missed completely at random. Multiple imputation ($m=20$) was performed on all demographic and outcome variables. Analyses were performed on each imputed dataset and the results were pooled using Rubin's rule. Robustness of the results was examined by comparing results before and after imputation.

Paired-samples t-tests were performed to examine the outcome changes from baseline to post-program in each study year across urban and rural settings. To estimate effect size, Cohen's d was calculated to describe program effects as small=0.20, medium=0.50, and large=0.80. To explore the program effects by year and setting, general linear model was employed by treating post-program outcome as the dependent variable, baseline outcome as the covariate, and study year and setting as the fixed factors. As this study was an exploratory pilot non-randomized trial aiming to generate the effect sizes for future confirmatory studies, multiple testing adjustments were not used.

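### No SAP test allows for the 13 centers; year and setting vary only between centers, so positive within-center correlation makes their p-values too small

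*SAP*

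**What the plan says.** The Protocol (Study Design, Setting, and Sample) states: "A one-group quasi-experimental study was conducted in 13 Michigan Head Start centers across two academic years". It gives the layout as "In Year 1, three urban Head Start centers (eight classrooms) and three rural Head Start centers (five classrooms) participated" and "In Year 2, four urban Head Start centers (five classrooms) and three rural Head Start centers (five classrooms) participated". In all, 107 dyads were enrolled from 23 classrooms. Table 1 of the Protocol shows that one of the three program components was delivered at the centers.

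The SAP (Data Analysis) lists these tests:
- independent-samples t-tests and Chi-square or Fisher's exact tests to compare years or settings;
- paired tests of change: "Paired-samples t-tests were performed to examine the outcome changes from baseline to post-program in each study year across urban and rural settings";
- a GLM with "post-program outcome as the dependent variable, baseline outcome as the covariate, and study year and setting as the fixed factors".

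None has a center or classroom term, a random effect, a cluster-robust standard error or a design effect. The sample-size text in the Protocol has no allowance for clustering either.

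The SAP calls the study an exploratory pilot "aiming to generate the effect sizes for future confirmatory studies, multiple testing adjustments were not used". That sentence covers multiplicity only. It says nothing about clustering.

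**The concern.** Families in one center share staff, classrooms and the center-based part of the program, so their outcomes may be correlated. Year and setting are properties of the center, not of the family. A GLM that counts families as independent then measures a between-center contrast against within-sample noise, with far more degrees of freedom than there are centers to support it. A nominally significant year or setting difference could be ordinary variation among 13 centers.

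The paired tests raise a narrower question. If the mean change is meant to inform studies in other centers, its precision should include between-center variation. The SAP's stated aim of supplying effect sizes for later confirmatory work makes this relevant.

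**Working it through.** **1. Layout.** Centers: Year 1 has 3 + 3 = 6 and Year 2 has 4 + 3 = 7, and 6 + 7 = 13 matches the stated total. So no center is in both years. Urban: 3 + 4 = 7. Rural: 3 + 3 = 6. Classrooms: 8 + 5 + 5 + 5 = 23, as stated.

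**2. Degrees of freedom.** The GLM has an intercept, baseline, year and setting: 107 − 4 = 103 residual df, if all 107 dyads are analysed and no interaction is fitted. At center level, intercept, year and setting leave 13 − 3 = 10 df.

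**3. Type I error of the GLM terms.** The ICC and the center sizes are assumptions. The GLM was simulated with no true year or setting effect, using 107 families and 10,000 trials per cell, under two layouts: near-equal centers (8 or 9 families each), and sizes following an assumed split of classrooms (14/14/9/9/9/5 in Year 1, 9/5/5/5/9/9/5 in Year 2). Rejection at nominal 5%, year / setting:

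| Center ICC | Near-equal sizes | Sizes by classrooms |
|---|---|---|
| 0 | 4.93% / 5.35% | 4.62% / 4.58% |
| 0.01 | 5.75% / 5.62% | 5.62% / 6.12% |
| 0.02 | 6.87% / 6.97% | 6.79% / 6.79% |
| 0.05 | 9.84% / 9.28% | 9.54% / 9.89% |
| 0.10 | 13.80% / 13.98% | 14.05% / 14.32% |

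A separate 10,000-trial run with the second layout gave 5.5/5.6% at 0.01, 9.3/9.6% at 0.05 and 14.9/14.5% at 0.10. A center-level analysis on 10 df stayed between 4.4% and 5.6% throughout.

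**4. Check by formula.** The design effect is 1 + (m − 1) × ICC, with m = 107/13 = 8.23. This gives 1.07, 1.14, 1.36 and 1.72 at the four ICCs. The actual level is about 2[1 − Φ(1.96/√design effect)] = 5.8%, 6.7%, 9.3% and 13.5%, in line with the simulation.

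**5. Sensitivity of the GLM terms (year / setting, 20,000 trials per cell, second layout).**
- Correlation at classroom rather than center level: 5.6/5.4%, 5.4/5.9%, 7.4/7.1% and 9.7/9.7%.
- Center-level correlation with 27.1% of families missing (the SAP's highest rate), complete cases: 5.7/5.5%, 6.3/6.1%, 8.1/8.1% and 11.4/11.4%.

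**6. By-year paired tests, if inference goes beyond these centers (Year 1 / Year 2, same layout).** 6.2/5.6%, 7.1/6.4%, 11.3/8.8% and 16.5/11.9%. They rest on 6 and 7 centers.

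**7. Power.** The stated figures reproduce. A two-sided paired t-test at 0.05 with d = 0.30 (noncentral t, noncentrality 0.30√N, N − 1 df) gives 80.4% at N = 90 and 85.1% at N = 102. These figures assume independent families and one test on the whole sample.

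Next, replace N in the noncentrality by N/[1 + (N/13 − 1) × ICC]. At ICC 0.05 and N = 90 this is 90/1.296 = 69.4; at N = 102 it is 102/1.342 = 76.0. The design effect is kept apart from the loss of df:

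| Center ICC | Design effect only, N − 1 df (N = 90 / 102) | Also on 12 df (N = 90 / 102) |
|---|---|---|
| 0 | 80.4% / 85.1% | 74.3% / 79.4% |
| 0.01 | 78.1% / 82.7% | 71.9% / 76.8% |
| 0.05 | 69.6% / 73.6% | 63.2% / 67.1% |

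Moving to a 12-df center-level test costs about 6 points by itself, even at ICC zero.

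**The case against.** The best reply has four parts.

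**The effect may be negligible.** No ICC is given. Two of the three components reach parents largely through Facebook, text messages, virtual meetings and private letters, so correlation by center may be slight. At ICC 0.01 the error rate is close to nominal, and classroom-level correlation does less harm than center-level correlation. This stands: the omission is certain, its size is not.

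**The study is an exploratory pilot whose product is effect sizes.** Mean change and Cohen's d are indeed not biased by ignoring center. But exploratory status does not correct a p-value, and the SAP invokes it only for multiplicity.

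**The SAP's exact procedure was not simulated.** The SAP specifies multiple imputation with 20 datasets, which "was performed on all demographic and outcome variables", pooled by Rubin's rule. The simulations used full data or complete cases. The 103 df is likewise conditional. Neither point puts center into the analysis.

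**Thirteen centers are few for cluster methods.** True, so a small-sample method is needed. No single one is obligatory.

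A reader might also infer three stronger claims, which are not supported:
- That any within-center correlation makes the p-values too small. Only positive correlation left after baseline adjustment does so. At ICC −0.02 the formula in step 4 gives about 3.4%, which is conservative.
- That clustering alone cuts power from 80% to 72% at ICC 0.01. Most of that drop is the switch to 12 df.
- That the by-year paired tests are wrong in any case. If inference is for these 13 centers only, they are not affected, and the documents do not state the target.

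**Conclusion.** The concern holds for the GLM year and setting terms. Followed as written, the SAP gives p-values for these terms that are too small whenever the baseline-adjusted outcome has positive within-center correlation. Type I error at nominal 5% is about 5-6%, 7%, 9-10% and 14-15% at center ICCs of 0.01, 0.02, 0.05 and 0.10. These ICCs and the center sizes are assumed; the two size layouts tried gave nearly the same result.

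For the by-year paired tests the concern is conditional on inference to other centers. The stated power figures are correct for independent families. With the design effect alone they become about 78% and 83% at ICC 0.01, and about 70% and 74% at ICC 0.05. The point bears on p-values and precision, not on the estimated changes themselves. It should be fixed, but it does not invalidate the study.

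**What to change.** Re-run the GLM year and setting tests with center as the cluster and a method suited to few clusters. Options are CR2 standard errors with Satterthwaite df, a center random intercept with small-sample df, or a center-level analysis. Center cannot simply be added as a fixed effect, because it would absorb year and setting. State whether inference is meant for these 13 centers or beyond them; if beyond, re-run the paired-change tests in the same way. Report the results beside the original ones, and state that the 80% and 85% power figures assume independent families.

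This uses data already held. The cost is wider intervals, even at ICC zero. With assumed by-year samples of 60 and 47 families and a standardized change (SD 1), the 95% half-width is t/√n. On 59 and 46 df it is 0.26 and 0.29; on 5 and 6 df (centers minus one) it is 0.33 and 0.36. CR2 df run slightly lower (about 4.5 and 5.5 on average in simulation), so its intervals would be marginally wider still. Some outcomes may lose nominal significance, and software other than SPSS 27 may be needed.
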